7.1.7 Safety Analysis

The first endpoint is to evaluate the toxicity of the proposed therapy. The first four months of therapy will be used as the time period in which toxicity will be evaluated and stopping rules for unacceptable toxicity will be implemented. Rules for stopping therapy will be based on rate of withdrawal due to significant toxicity (grade IV, non-hematological, non-metabolic and non-peripheral neuropathy). A true withdrawal rate within first 4 months of 15% will be considered excessive. Withdrawal rate will be assessed after every ten patients are treated. Enrollment will not be held though until the 10th patient enrolled becomes evaluable. Sufficient evidence will be taken for a lower limit to the corresponding one sided 80% confidence interval that exceeds 15%. Operationally observed rates that say regimen is too toxic would be 2/5, 3/10, 4/15, 5/20, 6/25 and 7/30. If the true probability of withdrawal from the study is 5%, the probability of deeming this regimen as too toxic after 15 or 30 patients have been treated is approximately .03 and .03, respectively. If the true probability of withdrawal is 10%, these probabilities are approximately .13 and .15, respectively. On the other hand, if the true probability of withdrawal is .30, then the probability of judging this regimen as too toxic after 15 or 30 patients is approximately .78 and .91, respectively.

With the semi-continuous monitoring of the withdrawal rate, the estimate of this rate, should the study run to completion, will be biased slightly downward. Without consideration of this bias, 30 patients will allow us 80% confidence that the estimated withdrawal rate will be within approximately .094 of the true rate under the assumption that the true rate is 20%. The incidence of second cancers will also be collected.

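### At the plan's own assumed 20% withdrawal rate, the monitoring bias that it calls slight and sets aside is about half the quoted .094 margin among completed studies

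*Combined protocol and SAP*

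**What the plan says.** All of the relevant text is in Section 7.1.7 (Safety Analysis). On semi-continuous monitoring it says that "the estimate of this rate, should the study run to completion, will be biased slightly downward". The next sentence opens with "Without consideration of this bias" and states that "30 patients will allow us 80% confidence that the estimated withdrawal rate will be within approximately .094 of the true rate". The rate is fixed as well: "under the assumption that the true rate is 20" percent.

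The monitoring rule has two descriptions in the same section. The text says "Withdrawal rate will be assessed after every ten patients are treated", while the boundary is listed in steps of five: "Operationally observed rates that say regimen is too toxic would be 2/5, 3/10, 4/15, 5/20, 6/25 and 7/30". Operating characteristics follow for true rates of 5%, 10% and 30%. At 5%, for example, "the probability of deeming this regimen as too toxic after 15 or 30 patients have been treated is approximately .03 and .03, respectively".

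Toxicity is the only primary endpoint (Sections 2.1 and 3.1). Section 7.1.1 gives 30 patients without a precision or power argument, so the .094 sentence is the only precision statement for that endpoint. No bias correction or sequential interval is specified.

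**The concern.** A rule that stops for too many withdrawals lets through to 30 patients only those studies that happened to see few. Their observed rate is therefore too low on average. The plan acknowledges this and its direction, but calls it slight and drops it when stating precision at a 20% rate. That rate is above the 15% that the plan treats as excessive, so the rule is working hard there and the selection effect should be large.

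At stake is how a completed study's withdrawal rate is read. With a true rate of 20%, a completer's estimate would centre near the 15% limit, and a reader would put a symmetric margin around it although the error runs almost wholly one way. Section 7.1.8 makes not being judged too toxic a condition for designing a phase III trial, so a completed study's rate is the one likely to be carried forward.

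**Working it through.** **Inputs (Section 7.1.7).** n = 30; true rate p = .20; 80% confidence, read as two-sided because the sentence says within (z = 1.2816); boundary 2/5, 3/10, 4/15, 5/20, 6/25, 7/30; looks every five patients (as the boundary is listed) or every ten (as the text says).

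**1. The plan's figure reproduces.** 1.2816 × √(.20 × .80/30) = 1.2816 × .0730 = .0936, or .094. A one-sided 80% multiplier would give .061, which does not fit.

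**2. Exact fixed-sample probability.** With X ~ Binomial(30, .20), being within .094 means 4 to 8 withdrawals (.133 to .267).
- P(4 ≤ X ≤ 8) = .749, with misses split .123 low and .129 high.
- P(3 ≤ X ≤ 9), that is within .10, = .895.

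**3. Which look schedule the plan used.** Let f_n(x) be the probability of x withdrawals among n patients with no stop so far. Then f_n(x) = (1 − p) f_{n−1}(x) + p f_{n−1}(x − 1). At each look before 30, states on or over the boundary are removed. The probability of declaring the regimen too toxic by 30 patients is:

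| True rate | Plan | Looks every 5 | Looks every 10 |
|---|---|---|---|
| 5% | .03 | .031 | .013 |
| 10% | .15 | .146 | .097 |
| 30% | .91 | .912 | .892 |

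After 15 patients, looks every five give .030, .129 and .775, against the stated .03, .13 and .78. The plan's figures therefore come from looks every five.

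**4. Studies that reach 30 patients, p = .20.** The distribution of withdrawals, given no earlier stop, is:

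| Withdrawals | 0–3 | 4 | 5 | 6 | 7 | 8 | 9 or more |
|---|---|---|---|---|---|---|---|
| Looks every 5 | .264 | .248 | .256 | .160 | .059 | .012 | .001 |
| Looks every 10 | .221 | .220 | .239 | .179 | .094 | .035 | .012 |

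| | Looks every 5 | Looks every 10 |
|---|---|---|
| Probability of reaching 30 | .438 | .545 |
| Mean estimate | .147 | .159 |
| Bias | -.053 | -.041 |
| Bias ÷ .094 | .56 | .44 |
| Bias ÷ .20 | 26% | 21% |
| Within .094 (4–8 withdrawals) | .734 | .767 |
| Miss low / miss high | .264 / .001 | .221 / .012 |

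**5. Bias among completers by true rate.**

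| True rate | Looks every 5 | Looks every 10 |
|---|---|---|
| 5% | -.002 | -.001 |
| 10% | -.011 | -.008 |
| 15% | -.028 | -.022 |
| 20% | -.053 | -.041 |

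**The case against.** The strongest reply is that the sentence claims little and what it claims is sound. It is labelled approximate, it fixes 30 patients and a 20% rate, it says that the bias is left out, and its number reproduces. All of that stands, and it rules out two stronger readings that a reader might infer.

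The first is that .094 is an arithmetic error because the exact probability is 75% rather than 80%. The documents do not support this. With 30 patients the estimate moves in steps of .033. Counts of 3 and 9 lie exactly .100 from .20, just outside the margin, so the probability jumps from .749 to .895 and no half-width gives 80% exactly. Applied at neighbouring rates, the same formula gives exact probabilities of .850 at 18%, .842 at 19%, .821 at 21%, .818 at 22% and .807 at 23%. The value at 20% is a local trough.

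The second is that the estimate falls within .094 in only about half of studies once the rule operates. The pooled figures are .468 (looks every five) and .505 (every ten), but they include studies stopped at 5 to 25 patients. A stop at 2/5, for instance, gives an estimate of .40. The sentence concerns 30 patients and does not cover those studies. Among studies that do reach 30, the probability is .734 or .767, close to the fixed-sample .749.

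Two further points also stand. The bias sentence is not itself tied to 20%, and slight is a fair word at 5% to 10%. Neither the stopping rule nor the phase III condition in Section 7.1.8 uses .094.

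None of this answers the remaining point. The precision statement is made at 20%, and at 20% the omitted bias is large relative to the quoted margin and changes the error from balanced to almost wholly low.

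**Conclusion.** The point holds as a weakness in how the primary endpoint's precision is stated and how its estimate will be reported. At a true rate of 20%, the bias among studies that reach 30 patients is -.053 with looks every five, the schedule that matches the stated operating characteristics, or -.041 with looks every ten. That is 44% to 56% of the .094 margin. Between 22% and 26% of completers miss low by more than .094, and about 1% or fewer miss high. Only 44% to 54% of studies would reach the 30 patients that the statement describes.

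The calculation assumes independent patients with a common withdrawal probability, a boundary applied exactly at each look, and immediate stopping. Section 7.1.7 does not hold enrolment while patients become evaluable, so some overrun is likely and the realised figures may differ.

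**What to change.** Four changes to Section 7.1.7:

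1. Label .094 as a fixed-sample normal approximation, and give the exact probabilities at 20%: .749 within .094 and .895 within .10. Add that 46% to 56% of studies would stop before 30 patients at that rate.
2. Replace the word slightly with the bias among completers by true rate: about -.01 at 10%, -.02 to -.03 at 15%, and -.04 to -.05 at 20%. A single figure without its rate would mislead.
3. Commit to reporting the final withdrawal rate with a named bias-adjusted estimate and an exact interval that accounts for the stopping boundary. State whether the adjustment is conditional on reaching 30 patients, as the plan's own bias sentence is, or averages over all stopping points.
4. Reconcile assessment every ten patients with the boundary listed every five, because the figures in items 1 and 2 depend on it, apart from the fixed-sample probabilities.

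The cost is a few sentences, a short exact calculation, a little more work at final analysis and a less favourable stated precision. The sample size and the listed boundary stay as they are. The only question of conduct is which look schedule applies, which the section must settle in any case.

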7.1.8 Interim Analysis

An interim analysis at 15 treated patients will be conducted to assess feasibility for maintenance therapy. If > 50% of patients are unable to receive > 50% of planned therapy in first 12 months of treatment, the study will be terminated due to lack of feasibility.

If this study regimen is deemed to be potentially efficacious and is not regarded as too toxic per stopping rules outlined above and observed EFS rate are consistent with rates that match or exceed historical benchmarks, then a phase III trial to show efficacy rate of this regimen over single agent therapy will be designed.

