Hypothesis of this phase II study is that ixazomib and lenalidomide as maintenance therapy after autologous PBSC transplant for Multiple Myeloma will be safe and tolerable and prolong the time to disease progression post transplant. The treatment regimen is alternating ixazomib with lenalidomide every two months until disease progression, intolerable toxicity or maximum of 24 months of therapy. The dose of ixazomib is 4.0 mg po on days 1, 8 and 15 per each 28-day cycle given for two consecutive months, followed by then lenalidomide 10 mg po daily for two consecutive months, then ixazomib for two months etc. Dose reduction for toxicity will be incorporated. If >30 days off initially planned next cycle of therapy, then patient will be taken off study. Toxicity will be graded per CTCAE version 4.0. The first four months of therapy will be used as the time period to evaluate end point of toxicity for stopping rules. Toxicity that meets stopping rules will be determined based on the number of patients that are withdrawn from study for significant toxicity (grade IV, non-hematological, non-metabolic, non-peripheral neuropathy) and the number of patients who stop therapy for toxicity and are withdrawn from study as they could not recover adequately and resume therapy by 30 days from the initial stopping of the study drugs. We shall consider the withdrawal rate to be excessive, and hence the therapy to be too toxic, if the true withdrawal rate from the study exceeds 15% in the first four months. An interim analysis at 15 treated patients will be conducted. If > 50% of patients are unable to receive > 50% of planned therapy in first 12 months of treatment, the study will be terminated due to lack of feasibility. Another endpoint is time to disease progression. Patients will be followed for initial response and for progression of disease, response criteria will be determined by International Myeloma working group criteria. In patients with chemo-refractory disease at the time of ASCT, the therapy will be felt to be promising if median time to progression is >9 months. If chemo-sensitive disease at time of ASCT, the therapy will be felt to be promising if median time to progression is >41 months based on CALGB 10014 lenalidomide maintenance study post ASCT. Cytogenetic information will be collected and initial response rates and outcome will be descriptively reported. Patients will be followed for overall survival. The incidence of secondary cancers will also be collected. If this study regimen is deemed to be potentially efficacious and is not regarded as too toxic per stopping rules outlined above and observed EFS rate are consistent with rates that match or exceed historical benchmarks, then a phase III trial to show efficacy rate of this regimen over single agent therapy will be designed.

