2.2 Secondary Objectives

- Evaluate the ability to deliver the planned therapy
- Assess initial response to therapy
- Evaluate the median time to disease progression
- Assess overall survival

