4.2 Number of Patients

Thirty patients. First day of treatment will define enrolled on study therapy.

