7.1.1 Determination of Sample Size

Thirty Multiple Myeloma patients post ASCT are to be enrolled over 2-3 years. Expect to enroll 1-1.5 patients per month.

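### The feasibility look is triggered at 15 treated patients but judges 12 months of therapy, with no rule for counting patients followed for less

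*Combined protocol and SAP*

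**What the plan says.** Section 7.1.8 sets the timing: "An interim analysis at 15 treated patients will be conducted to assess feasibility for maintenance therapy". It then gives the rule for the case in which more than half of the group proves "unable to receive > 50% of planned therapy in first 12 months of treatment, the study will be terminated due to lack of feasibility". The Protocol Summary repeats both: "An interim analysis at 15 treated patients will be conducted".

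Section 4.2 fixes when a patient counts: "First day of treatment will define enrolled on study therapy". Treated and enrolled are therefore the same count, and the 15th treated patient is the one who has just taken a first dose.

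Section 7.1.1 gives two statements on accrual: "Thirty Multiple Myeloma patients post ASCT are to be enrolled over 2-3 years" and "Expect to enroll 1-1.5 patients per month".

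For the four-month toxicity endpoint, section 7.1.7 does address immature follow-up: "Enrollment will not be held though until the 10th patient enrolled becomes evaluable". Section 7.1.8 has no counterpart. It does not say how long the 15 must have been followed, how a patient with less than 12 months counts, whether enrolment pauses, or whether the percentage refers to those 15 patients.

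**The concern.** The trigger and the quantity judged are on different clocks. The look is due when the 15th patient starts, but that patient's 12-month result may be open for another year. A team could judge the few patients with complete follow-up, or wait for all 15. The text supports neither choice over the other, and the two can lead to different decisions from the same trial.

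The first choice may leave almost nothing to judge. The second may bring the look so late that stopping spares few or no patients. What is at stake is the only stated decision rule for the first secondary objective in section 2.2: "Evaluate the ability to deliver the planned therapy".

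**Working it through.** **Inputs.** N = 30, 1-1.5 patients per month, and 2-3 years of enrolment (7.1.1); look at 15 treated, 12-month window, 50% thresholds (7.1.8); counted from first dose (4.2). Uniform accrual is assumed.

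**The plan's own figure.** The plan gives no operating figure for this look, only accrual. At the stated monthly rate, 30/1.5 = 20 and 30/1.0 = 30 months, against a stated 24-36 months. The period implies 30/36 = 0.83 to 30/24 = 1.25 per month. Both statements agree only at 1.0-1.25 per month; the full span is shown.

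**Formulas.** With rate r, patient i has been followed (15 - i)/r months when the 15th starts. Enrolment x months after that is min(30, 15 + x·r), if enrolment is not held.

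| Patients per month | 0.83 | 1.0 | 1.25 | 1.5 |
|---|---|---|---|---|
| Of 15, with 12 months when the 15th starts | 5 | 3 | 0 | 0 |
| Of 15, with 6 months then | 10 | 9 | 7 | 6 |
| Enrolled if the look waits for all 15 (x = 12) | 25 | 27 | 30 | 30 (33 before the cap) |
| Enrolments a stop then spares | 5 | 3 | 0 | 0 |

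**Decision threshold.** More than 50% of 15 is more than 7.5, so 8. Because 15 is odd, exactly one of two outcomes must occur: at least 8 failures or at least 8 successes. Acting on the first 8 certain results of either kind therefore gives the decision that full follow-up of the same 15 would give.

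**Gain when patients stop for good.** A patient who stops permanently at or below half of plan is a certain failure at that moment. If 8 or more of the 15 do so within 6 months of their own start, the eighth is known at the latest 6 months after the 15th starts, whatever the order:
- 15 + 6r = 20, 21, 22.5, 24 enrolled.
- Fewer than by waiting: 25 - 20 = 5, 27 - 21 = 6, 30 - 22.5 = 7.5, 30 - 24 = 6.

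**Gain when failing patients stay on therapy.** Let d be a constant share of scheduled therapy delivered (an assumption). Failure is certain once d·t + (12 - t) ≤ 6, that is, at t = 6/(1 - d) months.
- d = 0.2: t = 7.5; enrolled 21.25, 22.5, 24.4, 26.25; 3.75, 4.5, 5.6, 3.75 fewer than by waiting (about 4-6).
- d = 0.4: t = 10; enrolled 23.3, 25, 27.5, 30; 1.7, 2, 2.5, 0 fewer (0-2.5).
- d near 0.5: t approaches 12, and there is no gain.

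**Sensitivity to the halfway point.** Six months is a round figure. By cycles, half of 12 is 6 × 28 = 168 days, about 5.5 months. By doses, the plan is 6 × 3 + 6 × 28 = 186, and the 94th dose falls on day 194, about 6.4 months. Using 6.4 months gives 20.3, 21.4, 23.0 and 24.6 enrolled.

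**The case against.** The strongest reply is that the rule can be workable as written. The text does not require a 12-month wait, because inability to receive therapy can be certain earlier. If the first 8 patients are all on schedule, each passes half of plan at about 6 months, and the pass is settled at 8 + 6r = 13, 14, 15.5 or 17 enrolled, close to the stated trigger. This stands for a regimen that delivers well. It helps only if the protocol says patients may be classified that way, and it does not.

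Second, a passing trial saves no enrolments however early its patients are classified. This stands in full: the gain belongs only to trials in which at least 8 patients fail.

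Third, the toxicity rule in 7.1.7 already catches qualifying toxicity withdrawals in the first four months. This also stands. The feasibility rule adds something for stops for other reasons, later stops and slow delivery.

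Fourth, section 4.3 plans two years of follow-up after the last patient starts, so deliverability can be described in full at the end. True; only the early stop is affected. Quarterly completeness checks (7.1.4) and independent monitoring (section 10) supply no counting rule for it.

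Two stronger readings are tempting but unsupported. A reader might infer that the protocol commits to enrolling 25-30 patients before the look. It does not: the no-hold sentence covers the toxicity looks only, and with a hold the count would stay at 15, at the price of a pause in enrolment. A reader might also infer that a patient delayed by 30 days at every cycle would sit at the 50% line until month 12. Tables 6-1 and 6-2 step ixazomib down after delayed starts for toxicity, and repeated delays lead to discontinuation, so that course is not sustained.

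**Conclusion.** The gap is real and worth closing, though the gain is modest. At its stated trigger the look has 0-5 of 15 patients with the 12 months it judges (0-3 at the rates that fit both accrual statements). If it waits for all 15 without a hold, stopping spares 0-5 enrolments (0-3 at those rates).

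Classifying patients once certain keeps the 50% thresholds and the decision. It brings termination forward by 5-7.5 enrolments if at least 8 patients stop early for good, by about 4-6 if failing patients remain on therapy at 20% delivery, by 0-2.5 at 40%, and not at all near 50%.

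These figures assume uniform accrual, no enrolment hold and, for patients still on therapy, a constant share of delivery. The documents give no probability that 8 patients would fail. The 20-24 figure is the latest point in the early-stop scenario, not a floor: eight failures could be known sooner. Equivalence with full follow-up holds once planned therapy is defined.

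**What to change.** In 7.1.8, and in the matching text of the Protocol Summary, state that the rule applies to the first 15 treated patients. Then define:
- **Failure:** permanently discontinued with no more than 50% of planned 12-month therapy received, or still on therapy when more than 50% can no longer be reached by month 12.
- **Success:** more than 50% received.
- **Pending:** neither yet; resolved at month 12.

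Terminate for infeasibility at 8 certain failures; declare the rule passed at 8 certain successes. Say whether enrolment continues meanwhile. If a standing rule over all patients is meant instead, say so and give its denominator.

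Supporting definitions are needed to apply this: whether planned therapy is counted in cycles or doses, how delayed and reduced dosing count, and whether stopping for progression counts as inability to receive therapy. Sections 4.1 (24 cycles) and 6.1 (24 months) must be reconciled.

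The cost is a few sentences and a running tally; patient care does not change. Diaries (6.2), ixazomib pill counts (Schedule of Events) and recorded withdrawal reasons (6.15) are already planned. The scheduled pill counts do not cover lenalidomide, so those cycles would rest on the diary.

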8. ADVERSE EVENTS

8.1 Definitions

8.1.1 Pretreatment definitions

Patients will only be evaluable for adverse event reporting after received first dose of study drug.

8.1.2 Adverse Event Definition

Adverse event (AE) means any untoward medical occurrence in a patient or subject administered a pharmaceutical product; the untoward medical occurrence does not necessarily have a causal relationship with this treatment. An AE can therefore be any unfavorable and unintended sign (including an abnormal laboratory finding), symptom, or disease temporally associated with the use of a medicinal (investigational) product whether or not it is related to the medicinal product. This includes any newly occurring event, or a previous condition that has increased in severity or frequency since the administration of study drug.

An abnormal laboratory value will not be assessed as an AE unless that value leads to discontinuation or delay in treatment, dose modification, therapeutic intervention, or is considered by the investigator to be a clinically significant change from baseline.

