2. STUDY OBJECTIVES

2.1 Primary Objectives

- Evaluate the toxicity of the use of ixazomib and lenalidomide as maintenance therapy after autologous transplant

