4. STUDY DESIGN

4.1 Overview of Study Design

Treatment regimen

Alternating ixazomib 4.0 mg po on days 1, 8 and 15 per each 28- day cycle for two consecutive cycles, followed by then lenalidomide 10 mg po daily for two consecutive cycles until disease progression, intolerable toxicity or maximum of 24 cycles of therapy. Dose reduction for toxicity will be incorporated. If >30 days off initially planned next cycle of therapy, then patient will be taken off study. Toxicity will be graded per CTCAE version 4.0.

Therapy will start 30-120 days post autologous transplant when the patient is recovered from acute toxicity. See study flow chart on page 4 for scheduling of events for study.

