8.1.3 Serious Adverse Event Definition

Serious AE (SAE) means any untoward medical occurrence that at any dose:

- Results in **death**.
- Is **life-threatening** (refers to an AE in which the patient was at risk of death at the time of the event. It does not refer to an event which hypothetically might have caused death if it were more severe).
- Requires inpatient **hospitalization or prolongation of an existing hospitalization** (see clarification in the paragraph below on planned hospitalizations).
- Results in **persistent or significant disability or incapacity** (disability is defined as a substantial disruption of a person's ability to conduct normal life functions).
- Is a **congenital anomaly/birth defect**.
- Is a **medically important event**. This refers to an AE that may not result in death, be immediately life threatening, or require hospitalization, but may be considered serious when, based on appropriate medical judgment, may jeopardize the patient, require medical or surgical intervention to prevent 1 of the outcomes listed above, or involves suspected transmission via a medicinal product of an infectious agent. Examples of such medical events include allergic bronchospasm requiring intensive treatment in an emergency room or at home, blood dyscrasias or convulsions that do not result in inpatient hospitalization, or the development of drug dependency or drug abuse; any organism, virus, or infectious

particle (e.g., prion protein transmitting Transmissible Spongiform Encephalopathy), pathogenic or nonpathogenic, is considered an infectious agent.

Clarification should be made between a serious AE (SAE) and an AE that is considered severe in intensity (Grade 3 or 4), because the terms serious and severe are NOT synonymous. The general term *severe* is often used to describe the intensity (severity) of a specific event; the event itself, however, may be of relatively minor medical significance (such as a Grade 3 headache). This is NOT the same as *serious*, which is based on patient/event outcome or action criteria described above, and is usually associated with events that pose a threat to a patient's life or ability to function. A severe AE (Grade 3 or 4) does not necessarily need to be considered serious. For example, a white blood cell count of 1000/mm³ to less than 2000 is considered Grade 3 (severe) but may not be considered serious. Seriousness (not intensity) serves as a guide for defining regulatory reporting obligations.

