8.2 Procedures for Reporting Serious Adverse Events

AEs may be spontaneously reported by the patient and/or in response to an open question from study personnel or revealed by observation, physical examination, or other diagnostic procedures. Any clinically relevant deterioration in laboratory assessments or other clinical finding is considered an AE. When possible, signs and symptoms indicating a common underlying pathology should be noted as one comprehensive event. For serious AEs, the investigator must determine both the intensity of the event and the relationship of the event to study drug administration. For serious pretreatment events, the investigator must determine both the intensity of the event and the relationship of the event to study procedures.

AEs which are serious must be reported to Millennium Pharmacovigilance (or designee) from the first dose of study drug through 30 days after administration of the last dose of ixazomib. Any SAE that occurs at any time after completion of ixazomib treatment or after the designated follow-up period that the sponsor-investigator and/or sub-investigator considers to be related to any study drug must be reported to Millennium Pharmacovigilance (or designee). In addition, new primary malignancies that occur during the follow-up periods must be reported, regardless of causality to study regimen, for a minimum of three years after the last dose of the investigational product, starting from the first dose of study drug. All new cases of primary malignancy must be reported to Millennium Pharmacovigilance (or designee).

Planned hospital admissions or surgical procedures for an illness or disease that existed before the patient was enrolled in the trial are not to be considered AEs unless the condition deteriorated in an unexpected manner during the trial (e.g., surgery was performed earlier or later than planned). All SAEs should be monitored until they are resolved or are clearly determined to be due to a patient's stable or chronic condition or intercurrent illness(es).

Since this is an investigator-initiated study, the principal investigator [name] [name] also referred to as the sponsor-investigator, is responsible for reporting serious adverse events (SAEs) to any regulatory agency and to the sponsor- investigator's EC or IRB.

**Fred Hutchinson Cancer Research Center
Clinical Study Protocol [FHCRC 9266]**

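### The laboratory AE rule in section 8.1.2 lets some severe blood counts stay out of the descriptive toxicity data, and section 7.1.7 does not grade the counts themselves

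*Combined protocol and SAP*

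**What the plan says.** The primary objective (section 2.1) is to "Evaluate the toxicity of the use of ixazomib and lenalidomide as maintenance therapy after autologous transplant", and section 3.1 names toxicity as the only primary endpoint. Section 4.1 adds: "Toxicity will be graded per CTCAE version 4.0".

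Section 8.1.2 first gives a broad definition, under which an AE can be "any unfavorable and unintended sign (including an abnormal laboratory finding), symptom, or disease". It then narrows this for laboratory results: "An abnormal laboratory value will not be assessed as an AE unless that value leads to discontinuation or delay in treatment, dose modification", leads to a therapeutic intervention, "or is considered by the investigator to be a clinically significant change from baseline". Section 8.2 has a second statement: "Any clinically relevant deterioration in laboratory assessments or other clinical finding is considered an AE". Neither statement refers to a CTCAE grade.

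Section 8.1.3, in separating severity from seriousness, says that a white cell count of 1000/mm³ "to less than 2000 is considered Grade 3 (severe) but may not be considered serious".

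Section 7.1.7 bases its formal rule on withdrawals in the first four months. It does not say that scheduled laboratory results will be graded or tabulated.

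**The concern.** Blood-count toxicity matters in this trial. Section 1.10.1 gives overlapping toxicity of the two drugs and reduced marrow reserve soon after transplant as reasons for the modified schedule. The formal rule in section 7.1.7 leaves out grade IV haematologic events. Cytopenias that do not end in withdrawal can therefore be seen only in the descriptive AE data, and section 8.1.2 filters those data by action taken or by opinion rather than by grade. If a severe count can pass through unrecorded, the descriptive haematologic rate reflects the action limits and investigator discretion as well as the counts. A later reader deciding whether the toxicity profile is acceptable would be working from a figure that can err in only one direction.

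**Working it through.** **1. Can a count that the protocol calls Grade 3 miss every route into the AE data?** Take a white cell count of 1000 to <2000/mm³ found in mid-cycle.

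| Route | Source | What it requires | Must this count meet it? |
|---|---|---|---|
| Within-cycle hold | Tables 6-2 and 6.4 | ANC ≤500 or platelets ≤30,000/mm³, other than on Day 1 (for ixazomib, on a dosing day) | No. No white cell limit is given. Neutrophils are part of the white cell count, so this range is compatible with an ANC above 500. |
| Cycle-start delay | Sections 6.4.1 and 6.4.2 | On count grounds, ANC <1,000 or platelets <75,000/mm³ | No, if recovered by the next Day 1. |
| Late-cycle reduction | Table 6-2 | Haematologic toxicity after Day 15 dosing that recovers in time for the next cycle | Only for late events in ixazomib cycles. Table 6.4 has no matching row. |
| Intervention | Sections 8.1.2 and 6.7 | For example, transfusion or growth factor given | No, if untreated. |
| Judgement | Sections 8.1.2 and 8.2 | Investigator finds it clinically significant or relevant | No grade compels this. |

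Such a count can miss all five routes. The gap is limited to counts that meet four conditions together: above the hold limits, untreated, recovered by the next Day 1, and judged not significant.

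**2. Direction.** Let R be the number of the 30 patients whose counts reach Grade 3 or worse, and A the number of those recorded as having an AE for it. Recorded patients are a subset of R, so A ≤ R and A/30 ≤ R/30. The two are equal only if every such patient comes in by some route.

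**3. Size.** If c is the share captured, the undercount is R × (1 − c). The documents give no expected R for this regimen and no c. Over the full range of c from 0 to 1, the undercount runs from R down to 0. No narrower figure can be derived.

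**4. Does it reach the stopping rule?** The plan's own figures were reproduced first, by an exact binomial recursion:

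- P_n(k) = (1 − p)·P_{n−1}(k) + p·P_{n−1}(k − 1), removing the probability at or above the listed boundaries 2/5, 3/10, 4/15, 5/20, 6/25 and 7/30.

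| True withdrawal rate | Stated (15 / 30 patients) | Recomputed |
|---|---|---|
| 5% | .03 / .03 | .030 / .031 |
| 10% | .13 / .15 | .129 / .146 |
| 30% | .78 / .91 | .775 / .912 |

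The stated half-width of .094 also reproduces: 1.2816 × √(0.2 × 0.8/30) = .0936. (These probabilities need looks every five patients, whereas section 7.1.7 speaks of every ten; that is a separate matter.)

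The only inputs are the withdrawal probability and the boundaries. The count-based AE rate does not enter. A blood count that delays or stops treatment already meets section 8.1.2, and section 6.15 requires the reason for withdrawal to be recorded.

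**5. Are the data collected anyway?** From the Study Flow Chart, for a patient who completes 24 cycles:

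- CBC: 4 cycles × 4 (pre-dose, Days 8, 15, 22) + 20 cycles × 3 (pre-dose, Days 8, 15) = 16 + 60 = 76.
- Chemistry: 4 × 4 + 20 × 2 (pre-dose, Day 8) = 16 + 40 = 56.

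**The case against.** The strongest reply is that the toxicity decision does not use these data. The formal rule counts withdrawals for grade IV toxicity that is not haematologic, and the Protocol Summary adds failure to resume within 30 days. This stands. A reader might infer that section 8.1.2 weakens the stopping rule or its error rates; step 4 shows that it does not. What is affected is the descriptive part of the endpoint.

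Second, low counts have more ways in than the hold limits suggest. The late-cycle row of Table 6-2 carries no numerical cut-off, and supportive treatment counts as an intervention. This also stands. It would be wrong to say that every count above the hold limits leads to nothing.

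Third, section 8.1.3 offers its white cell example as a severe AE, and section 8.2 directs that clinically relevant deterioration be treated as an AE. This stands in part. The example distinguishes severe from serious and sets no recording rule; section 8.2 rests on judgement again. Neither obliges anyone to record a count because of its grade.

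Fourth, both drugs share the same within-cycle and cycle-start cut-offs, so a reader should not conclude that the two blocks cannot be compared. That is fair. The one visible difference is the late-cycle row, which Table 6.4 lacks. It is a reason to report by drug, and no more.

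Fifth, section 7.1.4 leaves the data items to case report forms that are not in the documents. They may well collect every count. Collection alone does not commit the analysis to grading them.

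**Conclusion.** The point holds in a limited form and should be fixed. As written, the plan allows some severe laboratory toxicity, including a count that it grades as severe itself, to be absent from the AE data in a trial whose primary endpoint is toxicity. The bias in the descriptive haematologic rate is downward or nil. Its size is unknown.

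Two stronger readings are tempting. One is to treat any ANC between the hold limit and the cycle-start limit (0.51-0.99 × 10⁹/L), or platelets of 31-74 × 10⁹/L, as missed Grade 3 toxicity. The documents give no CTCAE cut-offs for either count, and falling below a cycle-start limit is not a grade. The other is to put a number on the undercount using the 80% rate of Grade 3 or 4 haematologic toxicity in the appended lenalidomide label. That rate comes from del 5q myelodysplastic syndrome, a different disease, and a capture share would still have to be assumed.

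The conclusion rests on reading sections 8.1.2 and 8.2 as the only recording rules for laboratory AEs, and on section 7.1.7 as the whole of the planned safety analysis.

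**What to change.** Keep section 8.1.2 for reporting individual AEs and add to section 7.1.7:

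> Haematologic and chemistry toxicity will be graded by CTCAE 4.0 directly from every scheduled CBC and chemistry result, whether or not it meets 8.1.2, and summarised as worst grade per patient, overall and separately for ixazomib and lenalidomide cycles.

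The case report forms must then hold the scheduled values: at most 30 × 76 = 2,280 CBCs and 30 × 56 = 1,680 chemistry panels if all patients complete 24 cycles. No extra blood is drawn, and no dose rule, stopping boundary or sample size changes. The cost is data capture and programming. The reported Grade 3-4 laboratory toxicity rate is likely to be somewhat higher than under the AE rule alone, and the report should say that it is based on counts.
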